12.5.1 Analysis Population

All patients contributing both baseline measurement and 12-month follow up will define the efficacy population.

Missing data

In our primary analytical strategy, we proposed to employ the statistical analysis method widely known as the mixed effects modeling approach using the maximum likelihood (ML) estimation. The use of mixed effects modeling is critical in implementing the intention-to-treat principle and therefore maintaining the validity of our inferences in the presence of missing data. Data points that are missing due to attrition and nonresponse will be handled assuming that data are missing at random (MAR¹⁰⁰), conditional on observed information. We would like to emphasize that our method is less restrictive and therefore less likely to result in bias and misleading conclusions than alternative procedures utilizing missing completely at random (MCAR¹⁰⁰), assumed in fixed effects analyses such as ANOVA and regression analysis. In analyses utilizing MCAR, cases with missing information are simply excluded from the computations. By including every participant who completes at least one assessment in the analysis utilizing MAR, we are not only more likely to conserve power, but also less likely to produce biased effect estimates. Given the sizable sample and baseline covariates assessed, we believe mixed effects modeling using ML is a reasonable approach. Nonetheless, we are aware that the assumption of missing at random conditional on observed information can be somewhat violated in practice (because we cannot possibly collect every variable related to the missing data). To address this concern, we will conduct additional analyses at least for the key hypotheses (1 & 2) as a form of sensitivity analysis. For this purpose, we will apply the multiple imputation approach¹⁰¹ utilizing various auxiliary variables in the data. Additionally, we will conduct sensitivity analysis allowing for some deviation from MAR, for example assuming MAR conditional on intervention adherence status.^{97,102-104}

We recognize that the best way to handle missing data is to minimize the missing data during the study. To minimize missing data, our questionnaires will be collected electronically utilizing Qualtrics and having participants complete these assessments on either iPads or study computers, a strategy that we have now successfully piloted in our randomized clinical trial of bone marrow recipients, resulting in minimal missing data. If warranted, we will add another site to recruit additional patients. However, in our pilot study, attrition was about 8%, and missing data in the completers were very low (0 to 7%) for the key variables.

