12.4.1 Analysis Population

Include treatment of missing data and handling of non-adherence to protocol described in 12.4.2 and 12.5.1.

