12.4.2. Analysis Plan

For our primary Hypothesis 1, we will examine whether the BBT-I group will show more improvement, compared to the attention control group for insomnia symptoms measured by ISI from baseline to the 12-month follow-up. The group comparison will be made in line with the

Behavioral Intervention for Insomnia in Cancer

intention to treat principle. We will analyze the data using mixed effects (growth curve) modeling^{89,90} fully utilizing outcome data repeatedly measured four times for most participants (baseline, 6, 30, and 58 week). For estimation of mixed effect models, maximum likelihood (ML) estimation will be used. For ML estimation of these models, the Mplus program version 7.11 or above will be used.⁹¹ Data points that are missing due to subject attrition will be handled assuming that data are missing at random⁹² conditional on observed information, which is less restrictive than missing completely at random⁹² assumed in fixed effects analyses such as ANCOVA and regression analysis. In this procedure, all available cases including the ones with missing information will be included in the analyses. By including every subject who completed at least one assessment, we are not only more likely to conserve power, but also less likely to produce biased effect estimates. Given the sample and baseline covariates we will be collecting, we believe mixed effects modeling using ML is a reasonable approach. Nonetheless, we will conduct additional analyses at least for key hypotheses as a form of sensitivity analysis. For this purpose, we will apply the multiple imputation approach⁹³ utilizing various auxiliary variables in the data. We will conduct additional analyses allowing for some deviation from MAR, for example assuming MAR conditional on intervention adherence status.⁹⁴⁻⁹⁷

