12.5.2 Analysis Plan

The group comparison will be made in line with the intention to treat principle. We will analyze the data using mixed effects (growth curve) modeling^{89,90} fully utilizing outcome data repeatedly

Behavioral Intervention for Insomnia in Cancer

measured four times for most participants (baseline, 6, 30, and 58 week). For estimation of mixed effect models, maximum likelihood (ML) estimation will be used. For ML estimation of these models, the Mplus program version 7.11 or above will be used.⁹¹

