12.6.2 Sample size justification

For the primary Hypothesis 1 (BBT-I will show greater reduction of insomnia symptoms measured by ISI from baseline to the 12-month follow-up compared to the control), we estimated power in the proposed mixed effects modeling framework fully accounting for the longitudinal study design and projected attrition rate. The primary outcomes, ISI, will be measured at baseline, 6 weeks (end of treatment), 30 weeks, and 58 weeks (primary end point). For our power estimation, we used ML based mixed effects modeling assuming a linear trend. We assumed that at least 60% of variance is explained by the growth model for the primary outcome (i.e., reliability of 0.6), given that previous studies reported reliability ranging from 0.65-0.83.^{105,106} For attrition, we assumed gradually increasing attrition over time, resulting in 25% attrition by the 6-month follow-up assessment. We assumed a medium effect size, Cohen's d of 0.4 to 0.6, based on a previous study.¹⁰⁷ We also consider this range of effect size as the lower bound of a clinically meaningful treatment effect. Under this scenario, the estimated power to detect the group difference in change in ISI is 0.88-0.99 ($d=0.4$ to 0.6 , $\alpha=.05$, two-tailed) with $N=180$ (90 BBT-I, 90 control). We estimated power for the secondary Hypothesis 2 (BBT-I compared to the control will show greater improvements in fatigue and cognitive difficulties) using the same mixed effects modeling strategy. We assumed a moderate effect size of $d = 0.35$ to 0.4 , based on a previous study.^{108,109} We do not adjust for testing of multiple outcomes given that fatigue and cognitive difficulties are secondary outcomes. Under this scenario with reported reliability of 0.67 and higher,^{108,109} the estimated power to detect the group difference in change in BFI is 0.84-0.91 ($d=0.35$ to 0.4 , $\alpha=.05$, 2-tailed). For the mediator Hypothesis 3, we estimated power focusing on the main effect of the mediator on the outcome.^{98,99} We assumed a

Behavioral Intervention for Insomnia in Cancer

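### Section 12.5.1 restricts the efficacy population to patients with baseline and 12-month data, against the all-available-cases, intention-to-treat analysis described elsewhere in the same plan

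*Combined protocol and SAP*

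**What the plan says.** The sentence at issue opens section 12.5.1, under Secondary Analysis: "All patients contributing both baseline measurement and 12-month follow up will define the efficacy population".

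The missing-data text that follows in the same section takes the opposite line. It presents the mixed model as the means of achieving intention to treat and justifies it with the words "By including every participant who completes at least one assessment in the analysis utilizing MAR". It contrasts this with methods in which "cases with missing information are simply excluded from the computations".

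Section 12.5.2 then says: "The group comparison will be made in line with the intention to treat principle". For the primary hypothesis, section 12.4.2 also invokes intention to treat and adds that "all available cases including the ones with missing information will be included in the analyses". It later extends the same strategy to the secondary outcomes of Hypothesis 2.

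Section 12.4.1, the analysis-population section for the primary analysis, defines no set. Its whole content is: "Include treatment of missing data and handling of non-adherence to protocol described in 12.4.2 and 12.5.1".

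On the likely extent of missing data, section 12.6.2 assumes gradually rising dropout, "resulting in 25% attrition by the 6-month follow-up assessment", and section 12.5.1 reports pilot attrition of about 8%. No 12-month rate is given.

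**The concern.** The plan gives two incompatible answers to the question of who is analysed for efficacy. Having a 12-month value is an event after randomization, so a set defined by it no longer has the protection of randomization. Patients with only baseline, week-6 or week-30 data would be dropped. The mixed model would then be fitted to people who did not drop out, which defeats the plan's own reason for choosing it.

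The conflict is most direct for Hypothesis 2 (fatigue and cognition), which section 12.5 governs. For Hypothesis 1 it is weaker: 12.4.2 gives a full rule of its own, but 12.4.1 points to 12.5.1 as well. Two analysts could report different populations and each cite the plan.

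**Working it through.** **1. The rules side by side**

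| Data available | 12.5.1, opening sentence | 12.5.1 missing-data text and 12.4.2 |
|---|---|---|
| Baseline only | out | in |
| Baseline and week 6 | out | in |
| Baseline, weeks 6 and 30 | out | in |
| Baseline and week 58 | in | in |

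The rules disagree for every patient who leaves before week 58. The sensitivity analyses listed in 12.4.2 and 12.5.1 are multiple imputation and departures from missing at random. A completer analysis is not among them, and the term *efficacy population* is used nowhere else.

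**2. Patients affected**

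Retained = 180 × (1 − attrition).

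- At 25% (section 12.6.2): 180 × 0.75 = 135 kept, 45 dropped. The 25% is for 6 months, so 135 is a maximum at 12 months, provided that nobody who misses 6 months returns.
- At 8% (pilot, assumed to apply at 12 months): 180 × 0.92 = 165.6, about 166 kept and 14 dropped.

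**3. Power**

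The plan states 0.88 to 0.99 for d = 0.4 to 0.6. It does not give the variance components or the scale of d, so this cannot be reproduced with certainty. One reading of its reliability of 0.6 is between-person variance 0.6 and residual variance 0.4 (total 1), with visits at weeks 0, 6, 30 and 58 and an effect linear in time. Adding assumed retention of 95% at week 6 and 75% at weeks 30 and 58, with a common baseline mean, gives a standard error of 0.1286. Power is then Φ(0.4/0.1286 − 1.96) = Φ(1.15) = 0.875, and Φ(0.6/0.1286 − 1.96) = Φ(2.71) = 0.997. This is close to the plan's figures.

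The same set-up at d = 0.4, with dropout at random:

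| Model | All available | 135 completers |
|---|---|---|
| Linear, common baseline | 0.875 | 0.874 |
| Linear, separate baselines | 0.836 | 0.826 |
| Visit-specific means, separate baselines | 0.770 | 0.738 |

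The loss is 0.1 to 1.0 points in the linear model and about 3 points with visit-specific means. At 92% retained it is under one point.

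**4. Bias (illustration)**

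Same variances; true effect linear to −0.40 SD at week 58; dropouts lose weeks 30 and 58. Assumed: dropout in BBT-I rises with week-6 ISI (log-odds 0.5 or 1.0 per SD), and dropout in the control arm is random. Estimates of the week-58 contrast from large simulated samples:

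| Analysis | 75% retained (0.5; 1.0) | 92% retained (0.5; 1.0) |
|---|---|---|
| Completers, linear, separate baselines | −0.372; −0.360 | −0.390; −0.385 |
| Completers, linear, common baseline | −0.404; −0.414 | −0.401; −0.404 |

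Across all settings, the completer change score gave −0.396 to −0.399 and the linear model on all available data gave −0.396 to −0.402.

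The direction of bias depends on the model and on who leaves. The change score escapes because, in this set-up, selection on week 6 shifts the baseline and week-58 means equally. When dropout depends on week-6 ISI in the same way in both arms, the completer estimates return to −0.397 to −0.402.

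**The case against.** The strongest reply is that the plan largely answers the question itself. One sentence stands against several reasoned statements in 12.4.2, 12.5.1 and 12.5.2; the power calculation models attrition within a mixed model; and 12.4.2 carries its strategy to Hypothesis 2. No analysis is assigned to the efficacy population, so it can be read as a leftover label. For the primary analysis, 12.4.1 refers to 12.5.1 for missing data and non-adherence, and the missing-data text there is the all-available-cases text. The bias also needs dropout that differs between arms, which nothing in the documents predicts, and even then the largest shift is 0.04 SD.

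Much of this stands. The surrounding text favours all available cases, the primary analysis is only weakly touched, and the numerical consequences are modest. What does not stand is the reading of the sentence as a harmless extra. It is the only definition under the Analysis Population heading of 12.5.1, it is called the efficacy population, and nothing marks it as supportive. No reading reconciles it with the paragraph beneath it.

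**Conclusion.** The concern holds and should be fixed. It rests on the text: the completer definition contradicts the inclusion rule in its own section and the intention-to-treat analyses in 12.4.2 and 12.5.2. Depending on which sentence is followed, about 14 to 45 or more of 180 randomized patients move in or out of the analysis. This assumes that dropouts do not return and, for the lower figure, that the pilot's attrition applies at 12 months.

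The bias illustration, with shifts of up to 0.04 SD on an effect of 0.40 SD and in either direction, depends on dropout related to ISI in one arm only. It shows what could happen and is not a forecast. The primary result is not in doubt if 12.4.2 is followed as written.

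**What to change.** Delete the opening sentence of 12.5.1, or relabel it as a completer set for supportive analysis only. In both 12.4.1 and 12.5.1, state that the efficacy population for Hypotheses 1 and 2 is all randomized participants, analysed in the arm to which they were assigned, using every available assessment. In 12.4.1 this should replace the present cross-reference as the definition of the population.

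The cost is a wording change to the statistical section. The planned maximum-likelihood mixed model already accommodates incomplete cases, so the model, sample size and data collection are unaffected.

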12.5.2 Analysis Plan

The group comparison will be made in line with the intention to treat principle. We will analyze the data using mixed effects (growth curve) modeling^{89,90} fully utilizing outcome data repeatedly

Behavioral Intervention for Insomnia in Cancer

measured four times for most participants (baseline, 6, 30, and 58 week). For estimation of mixed effect models, maximum likelihood (ML) estimation will be used. For ML estimation of these models, the Mplus program version 7.11 or above will be used.⁹¹

12.6 Sample Size

12.6.1 Accrual estimates

Stanford Cancer Center sees approximately 500 new breast cancer patients per year and about 341 patients (Range 318-376) are currently undergoing chemotherapy per STRIDE database. In our pilot, we were able to recruit a new participant every week. Thus, we anticipate that we would be able to meet our recruitment goal within 4 years even after accounting for attrition.

To minimize attrition, we will schedule participants for assessments during their clinic days. We budgeted funds for participants' travel, parking, and refreshments to improve retention. We will maintain close contact with participants with letters and projects updates, call or email (based on their preference) to remind participants to follow the study procedures. We also will send birthday cards and provide recruitment updates on our website to keep participants interested throughout the duration of the study. The proposed study involves a lower participant burden than our pilot that required more follow-ups, longer actigraphy and saliva collection and more measures. We found that we were able to minimize attrition in our current pilot with the above mentioned strategies. We will work closely with the Breast Cancer Connections advocacy group as we have done in the past, to provide training to our staff to ensure supportive and rewarding experiences for our participants. We will monitor our accrual closely and based on our current experience, we anticipate being able to recruit our participant sample. However, if we are unable to meet our recruitment target during the first year, we will expand our recruitment area to other local oncology clinics.

12.6.2 Sample size justification

For the primary Hypothesis 1 (BBT-I will show greater reduction of insomnia symptoms measured by ISI from baseline to the 12-month follow-up compared to the control), we estimated power in the proposed mixed effects modeling framework fully accounting for the longitudinal study design and projected attrition rate. The primary outcomes, ISI, will be measured at baseline, 6 weeks (end of treatment), 30 weeks, and 58 weeks (primary end point). For our power estimation, we used ML based mixed effects modeling assuming a linear trend. We assumed that at least 60% of variance is explained by the growth model for the primary outcome (i.e., reliability of 0.6), given that previous studies reported reliability ranging from 0.65-0.83.^{105,106} For attrition, we assumed gradually increasing attrition over time, resulting in 25% attrition by the 6-month follow-up assessment. We assumed a medium effect size, Cohen's d of 0.4 to 0.6, based on a previous study.¹⁰⁷ We also consider this range of effect size as the lower bound of a clinically meaningful treatment effect. Under this scenario, the estimated power to detect the group difference in change in ISI is 0.88-0.99 ($d=0.4$ to 0.6 , $\alpha=.05$, two-tailed) with $N=180$ (90 BBT-I, 90 control). We estimated power for the secondary Hypothesis 2 (BBT-I compared to the control will show greater improvements in fatigue and cognitive difficulties) using the same mixed effects modeling strategy. We assumed a moderate effect size of $d = 0.35$ to 0.4 , based on a previous study.^{108,109} We do not adjust for testing of multiple outcomes given that fatigue and cognitive difficulties are secondary outcomes. Under this scenario with reported reliability of 0.67 and higher,^{108,109} the estimated power to detect the group difference in change in BFI is 0.84-0.91 ($d=0.35$ to 0.4 , $\alpha=.05$, 2-tailed). For the mediator Hypothesis 3, we estimated power focusing on the main effect of the mediator on the outcome.^{98,99} We assumed a

Behavioral Intervention for Insomnia in Cancer

moderate correlation between the hypothesized mediators and the outcome ($r=0.2$ to 0.3). We do not adjust for testing of multiple mediators given our concerns in failing to detect possible mediators due to insufficient power (note that our trial is powered based on our primary hypothesis). Under this scenario, the estimated power to detect the mediation effect is $0.76-0.99$ ($r=0.2$ to 0.3 , $\alpha=.05$, two-tailed). For all hypotheses, we will carefully monitor both statistical (i.e., p-value) and clinical (i.e., effect size) significance, with more emphasis on clinical significance in the secondary hypotheses.

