10. MEASUREMENTS

For clinicaltrials.gov and Stanford Clinical Trials Directory compliance

Primary Outcome Measure Insomnia.

- **Title:** Insomnia Severity Index
- **Time Frame:** Pre, post intervention and at 6 and 12 months follow-ups.
- **Safety Issue:** No

Note: Each outcome measure listed within the protocol will necessitate legally required results reporting to clinicaltrials.gov within one year after the completion of the primary outcome measure.

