10.1 Primary and Secondary Outcome measures

Primary Outcome Measure of Insomnia. The effects of the BBT-I intervention on insomnia will be measured by the Insomnia Severity Index (ISI), which is a well-validated self-report measure of sleep.⁶⁰⁻⁶² The primary outcome will be the change from baseline to 6-month follow-up. A change score of -6 is considered a minimally clinically significant difference for the ISI.⁶⁰⁻⁶² The measure consists of seven questions on a 5-point Likert Scale with a total score ranging from 0-28. Reliability and validity of this measure have been established.⁶⁰⁻⁶² The ISI is the primary outcome measure for the study.

Secondary Outcome: Fatigue will be assessed with the revised Brief Fatigue Inventory (BFI), a 9-item, patient-report instrument that we have used in previous studies with established reliability and validity.⁶³ The BFI allows for rapid assessment of fatigue level in BC patients and identifies those with severe fatigue.

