12.4 Primary Analysis

Aim 1 (Primary): To evaluate the efficacy of the BBT-I in treating insomnia among breast cancer patients receiving chemotherapy.

Hypothesis 1 (Primary): BBT-I compared to an attention control group, will be associated with greater reduction of insomnia symptoms (as measured by the Insomnia Severity Inventory) from baseline to the 12 month follow up.

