In our mixed effects analyses, the change in the outcome will be modeled as the key dependent variable predicted by the treatment status. The results of these longitudinal analyses can be easily converted to treatment effect at each assessment point to directly respond to our specific hypotheses. In particular, we are interested in the main effect of treatment (BBT-I vs. Control) at 12-month follow-up (58 week) assessment. The same analysis strategy will be employed for Hypothesis 2, where we will examine the treatment effects on secondary outcomes such as fatigue (measured by BFI) and cognitive difficulties (measured by Cognitive Battery). In Hypothesis 3, we will examine the mediators of treatment effects on insomnia, fatigue, and cognitive difficulties.

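### The protocol names two primary time points for the ISI, 6 months in section 10.1 and 12 months in the hypothesis, analysis and power sections, and section 12.6.2 gives no attrition figure for the 12-month visit

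*Combined protocol and SAP*

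**What the plan says.** Section 10.1, which defines the outcomes, says of the Insomnia Severity Index (ISI): "The primary outcome will be the change from baseline to 6-month follow-up".

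Other sections use 12 months:

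- Section 12.4, Hypothesis 1: "greater reduction of insomnia symptoms (as measured by the Insomnia Severity Inventory) from baseline to the 12 month follow up".
- Section 12.4.2, on the group comparison: "insomnia symptoms measured by ISI from baseline to the 12-month follow-up".
- Section 12.4.2, on the contrast: "we are interested in the main effect of treatment (BBT-I vs. Control) at 12-month follow-up (58 week) assessment".
- Section 12.6.2 lists the four visits and labels the last one "58 weeks (primary end point".
- Section 12.5.1 defines its efficacy population by a baseline and a 12-month measurement.

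The outcome entry at the start of section 10 does not choose. Its time frame is "Pre, post intervention and at 6 and 12 months follow-ups". The Procedures paragraph of section 4 equates 6 months with week 30 and 12 months with week 58.

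On power, section 12.6.2 assumes a linear trend and a reliability of 0.6 ("We assumed that at least 60% of variance is explained by the growth model for the primary outcome"). On attrition it says: "we assumed gradually increasing attrition over time, resulting in 25% attrition by the 6-month follow-up assessment". It gives no figure for week 58. The resulting power, repeated in the synopsis, is 0.88-0.99 for d=0.4 to 0.6 with 90 patients per arm and two-sided alpha 0.05.

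**The concern.** A single primary time point is fixed in advance so that the choice cannot be made after the results are known. Here the section that defines the outcome and the sections that test it disagree. Section 12.4.2 adds that the longitudinal model can be turned into a treatment effect at each assessment, so both a week-30 and a week-58 estimate will exist. Each could be called primary with support from the text.

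The power statement has a secondary gap. It is written for week 58, but attrition is quantified only to week 30, in a sentence that describes loss as rising over time. Three readings are open: 25% is also the total at week 58, with no loss after week 30; 6 months is a slip for 12 months; or later loss was left out. A reader cannot tell which one underlies the 0.88.

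**Working it through.** **The time point.** This needs no arithmetic. Section 10.1 says 6 months, which is week 30 by section 4. Sections 12.4, 12.4.2 and 12.6.2 say 12 months, which is week 58. The labels cannot mean the same visit, and nothing in the document gives one section precedence over another.

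**The power figure.** The question is whether 0.88 fits the stated inputs, and how far it would move with loss after week 30.

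Inputs from section 12.6.2: visits at weeks 0, 6, 30 and 58; 90 per arm; linear trend; reliability 0.6; 25% lost by week 30; d=0.4 or 0.6; two-sided alpha 0.05.

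Inputs assumed because the plan does not give them: random intercept only (no slope variance), equal baseline means, d measured in baseline SDs at week 58, monotone dropout, and 95% retained at week 6.

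Model, with time t = week/58, arm A = 0 or 1 and total baseline variance 1:

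- Y = b0 + u + (b1 + δA)t + e, with Var(u) = reliability and Var(e) = 1 − reliability.
- SE(δ) is the square root of the δ element of the inverse of Σ X′V⁻¹X, summed over patients according to the visits each one has.
- Power = Φ(d/SE − 1.96). The opposite tail is negligible.

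The plan's own figure, at reliability 0.6:

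- 25% lost by week 30 and none later: SE = 0.1286. For d=0.4, 0.4/0.1286 = 3.11 and Φ(3.11 − 1.96) = 0.875. For d=0.6, power is 0.997.
- Loss rising in a straight line to 25% at week 58: SE = 0.1262. For d=0.4, 0.4/0.1262 = 3.17 and Φ(3.17 − 1.96) = 0.887. For d=0.6, power is 0.997.

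Both are close to the stated 0.88-0.99, so the figure is attainable but does not show which reading was used.

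If loss continues after week 30 (the week-58 percentages are assumed), power at d=0.4 is:

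| Lost by week 58 | SE, reliability 0.6 | Power | SE, reliability 0.65 | Power |
|---|---|---|---|---|
| 25% | 0.1286 | 0.875 | 0.1216 | 0.908 |
| 30% | 0.1319 | 0.858 | 0.1248 | 0.893 |
| 35% | 0.1356 | 0.839 | 0.1282 | 0.877 |
| 40% | 0.1395 | 0.818 | 0.1320 | 0.858 |

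Reliability 0.65 is the lowest value that section 12.6.2 cites from earlier studies. At d=0.6, power is at least 0.99 in every cell.

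Other unstated inputs matter as much. At reliability 0.6 with no later loss and d=0.4, a slope variance of 0.05 or 0.10 (58-week unit, uncorrelated with the intercept) gives 0.846 or 0.818. Estimating a separate baseline difference gives 0.836.

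**The case against.** The strongest reply is that the text leans heavily one way. Hypothesis, analysis, contrast, power and the efficacy population in 12.5.1 all point to 12 months, and the sentence in 10.1 stands alone. The list of visits in section 10 is normal for a repeated measure and contradicts nothing. This stands, and it shows which edit is easiest. It does not remove the conflict, because the lone sentence sits where the primary outcome is defined.

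A second reply is that the planned model uses all visits, so the choice matters less than it seems. A reader might reason that under a linear trend d=0.4 at week 58 is only 0.4 × 30/58 = 0.21 at week 30, and infer that a 6-month primary would be underpowered. The plan does not support that. In the same model the standard error shrinks by the same factor, 0.1286 × 30/58 = 0.0665, and 0.207/0.0665 is again 3.11. Test and power are identical, and only the reported estimate differs. However, the linear trend is stated for the power calculation only. Section 12.4.2 does not fix the shape of the curve, so the two tests need not coincide in the analysis.

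A reader might also infer from section 3.5 that 6 months was meant, since primary completion is set at 48 months. At the pilot rate of one recruit a week (12.6.1), the last week-30 visit falls at 180 + 30 = 210 weeks, or 48.3 months, and the last week-58 visit at 238 weeks, or 54.7 months. But 12.6.1 allows up to 4 years for accrual. On that basis the last visits fall at about months 54.9 and 61.3, and neither fits. The timeline does not settle the question.

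Finally, 25% is already about three times the pilot attrition of about 8% (12.5.1), and the documents give no source for 30-40%. That is fair, although they do not show that the pilot followed patients for as long. The higher losses above are illustrations, not forecasts.

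**Conclusion.** The contradiction over the primary ISI time point is certain, because it rests on the text alone. It should be resolved before results are available.

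The attrition gap is real but secondary. That it arises from the same 6-month/12-month confusion is an inference. A reader might conclude that the 0.88 is wrong or the trial too small. Neither follows: two of the three readings of the attrition sentence give 0.875 and 0.887 in a random-intercept linear model with equal baselines and 95% retained at week 6. If 30-40% were lost by week 58, power at d=0.4 would be about 0.86-0.82 at reliability 0.6 or 0.89-0.86 at 0.65. That is modest, and no larger than the effect of inputs the plan leaves unstated.

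**What to change.** 1. Name one primary ISI time point and use it in sections 10, 10.1, 12.4, 12.4.2 and 12.6.2. Keeping week 58 needs the fewest edits: change the sentence in 10.1 and mark the 12-month visit as primary in the section 10 outcome entry.
2. In 12.6.2, state the attrition assumed at that visit. If it exceeds 25%, rerun the calculation and restate power at d=0.4 there and in the synopsis.

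The cost is a few wording changes and at most one rerun. Stated power at d=0.4 may drop by a few points. No additional patients are needed.
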